## **IV. Research Methods**

### **A. Outcome Measures/Study Endpoints**

Primary Endpoint - Rate of VZV DNAemia after ID vOka challenge.

Secondary Endpoint – Duration and magnitude of VZV DNAemia and rate of VZV RNAemia. VZV- and gE-specific T cell and other immune cell responses in blood and at the site of ID vOka challenge; cytokines levels in blood and at the site of ID vOka inoculation; transcriptomics of immune cells in blood and skin biopsies; immunohistochemistry of skin biopsies of the ID vOka challenge.

Exploratory Endpoint –After RZV: Tetramer analysis of the T cell responses; T cell epigenome.

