## C. Study Design and Research Methods

### **Part A; Cohorts 1 and 2**

Seventy subjects with documented evidence of a HZ vaccine at least 5 years previously, divided equally between recipients of ZVL (Cohort 1) or RZV (Cohort 2) - 35 in each group - will be enrolled. Participation will consist of 4 visits over the course of 7-10 days in which blood is drawn, a challenge dose of vOka is given, and a skin biopsy is obtained.

ID vOka challenge live attenuated VZV (as 1 dose of licensed ZVL; Zostavax) will be prepared by mixing 0.35 ml of accompanying diluent with the vaccine and injecting 2 side-by-side intradermal doses of 0.125ml each, for a total of 0.25 ml (about  $\frac{3}{4}$  of the normal dosage or 13,857 plaque forming units) intradermally in the non-dominant deltoid region, using a NanoPass MicronJet600 device, on D0. Blood (60 ml) will be drawn prior to vaccination (D0), and at Days 1, 3, and 7. A skin biopsy (4 mm punch biopsy) will be done at the injection site, on the first 20 subjects (up to 25, if replacements needed) in each vaccine group; five each of these 20 will be biopsied on Day 0, 1, 3, or 7 in the order in which the participants enter the study. The Day 0 biopsy will be done on the contralateral arm in the deltoid region prior to vaccination. Initially every subject enrolled will be required to do the biopsy; this is reflected in the consent. The consent form will be amended to remove references to the biopsy procedure once the number of subjects needed for the biopsies is reached.

Subjects in the ZVL group will be offered RZV vaccine (to comply with ACIP recommendations for shingles immunization), to be administered beginning  $\geq$  60 days after Day 0. If subject wishes to receive the RZV vaccine, 2 additional visits will be required at Day 60 and Day 120, increasing the duration of participation up to 4 months. Subjects will not be reimbursed for these visits but will receive the vaccine free of charge.

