### **Schedule of Events – Cohorts 1 & 2**

Cohorts 1 and 2 ZVL/RZV > 5y previously	Visit 1	Visit 2	Visit 3	Visit 4	Phone	Visit 5	Visit 6
	Day 0	Day 1	Day 3	Day 7 (+3)	+ 48 hour after V4	Day 60 (+30)	Day 120 (+30)
Informed consent, review of eligibility criteria	•						
Medical history and current medications	•					• 	• 
Blood draw (60ml)	•	•	•	•			
Pre-vaccination body temperature	•					• 	• 
Vaccination (ID vOka challenge)	•						
Punch biopsy of ID challenge site 	•  , or	•  , or	•  , or	• 			
Vaccination – Dose 1 RZV 						• 	
Vaccination – Dose 2 RZV 							• 
AE assessment	•	•	•	•	•		

40 subjects (20 in each vaccine group) with 5 each at one of the time points identified

Contralateral site only

If prior ZVL

Recruitment – There are very few people in the world who had RZV administered 5 years previously. These subjects will come from an experiment done here (COMIRB #13-3192) in which we compared immune responses to RZV and ZVL. The 4y post-vaccination samples are being collected this year, and the 5y sampling will be completed between Nov 2019 and Mar 2020. When these older vaccinees complete 5y after immunization, they will constitute a unique population eligible for our proposal. To secure participation for this proposal, we will contact participants in our current trial (who had consented to be contacted about future clinical trials).

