We will generate descriptive tables of response and compare soluble factors and phenotypic markers between the 2 groups using multivariate analysis methods. We will use Hotelling's T2 test for the flow cytometric and soluble factors. We will adjust the outcome measures for potential confounders and redo the T2 test. If necessary, outcome measures will be log-transformed in order to better satisfy the assumptions of the T2 method. Cross sectional pairwise comparisons of gene expression will be made at 0, 1, 3 and 7d between groups using the DESeq2 package. Genes differentially expressed at day 0 will be filtered out at subsequent time points to avoid confounders unrelated to the intervention. Differentially expressed genes of interest at 1, 3 or 7d will be validated by RT-qPCR and used as input for downstream gene ontology pathway analysis. We will use the lists from each time point to investigate trends in gene expression over time (e.g. Is gene A upregulated at all time points?). Due to the large number of tests, False discovery rate (FDR) will be controlled at the level of 0.05.

For analysis of soluble markers and relationship to transcriptomic results:

We will generate descriptive tables of vOka replication and immune responses from all parameters by vaccine groups. We will use generalized linear models (GLM) to identify correlates between local vOka replication and viremia and between local and systemic APC, NK and Tconv, soluble markers and gene expression. Correlations will be examined between biopsies and systemic data collected at the same, preceding, and following time points. We will adjust for age and gender as appropriate and use FDR p-values.

For analysis of systemic and local immune responses that limit viremia:

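### Part A biopsy day follows order of entry, with no randomisation and no stated sequence; if days fill in consecutive fives, between-day skin comparisons are confounded with enrolment order.

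*Combined protocol and SAP*

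**What the plan says.** Section IV.C (Part A; Cohorts 1 and 2) takes a punch biopsy "on the first 20 subjects (up to 25, if replacements needed) in each vaccine group". Five of each 20 "will be biopsied on Day 0, 1, 3, or 7 in the order in which the participants enter the study". Footnote 1 to the Schedule of Events for Cohorts 1 and 2 confirms one time point per person: "40 subjects (20 in each vaccine group) with 5 each at one of the time points identified". The Day 0 sample comes from a different site: "The Day 0 biopsy will be done on the contralateral arm in the deltoid region prior to vaccination".

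No random allocation of day is described and no reason is given for using entry order. The protocol does not say whether the first five entrants all have Day 0, the next five Day 1 and so on, or whether the days rotate person by person. Nor does it say which day a replacement takes.

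Section IV.A lists "immunohistochemistry of skin biopsies of the ID vOka challenge" and transcriptomics of skin biopsies among the secondary endpoints. In section IV.G, the paragraph on soluble markers and transcriptomic results states: "Correlations will be examined between biopsies and systemic data collected at the same, preceding, and following time points". On covariates it adds: "We will adjust for age and gender as appropriate and use FDR p-values". Entry order and calendar time are not among the adjustment variables.

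**The concern.** With one biopsy per person, the skin time course rests wholly on comparing one set of five people with another. Such a comparison is fair only if the sets are alike apart from the day. Random allocation secures that on average; entry order does not.

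Entry order could plausibly carry information. The long-term RZV recipients come from one earlier study and become eligible as they reach five years; the recruitment paragraph says "the 5y sampling will be completed between Nov 2019 and Mar 2020". If the recruitment mix or the measurements shift over enrolment, and if days are filled in consecutive fives, that shift would look like a change from Day 0 to Day 7. Correlations of skin with blood would be open to the same problem if pooled across days. The plan does not say whether they will be, but five people per day and group leave little room for day-by-day correlations.

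Under any fixed sequence, staff also know the next day in advance and could time a participant's entry around it.

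**Working it through.** **Inputs from the protocol.** Five per day, four days and two groups (IV.C; Schedule of Events footnote 1). Check of the plan's own count: 5 × 4 = 20 per group, and 20 × 2 = 40, as stated.

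**Assumed input.** The documents give no figure for drift in a skin measure over enrolment. I take a linear drift of d = 0.5, 1 or 2 SD from the 1st to the 20th entrant, no true effect of day, and a residual SD of 1.

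**Step 1: mean entry position by day.**
- Consecutive fives: 3, 8, 13 and 18 for Days 0, 1, 3 and 7.
- Rotation: 9, 10, 11 and 12.

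**Step 2: how far day and entry order coincide.** R-squared is the between-day sum of squares of entry position divided by the total. The overall mean is 10.5 and the total is 20 × (20² − 1)/12 = 665.
- Consecutive fives: 5 × (7.5² + 2.5² + 2.5² + 7.5²) = 625, so 625/665 = 0.94.
- Rotation: 5 × (1.5² + 0.5² + 0.5² + 1.5²) = 25, so 25/665 = 0.04.
- Simple randomisation, expected value: 3/19 = 0.16 (simulated 95% range 0.01 to 0.44).
- Permuted blocks of four: about 0.007 on average by simulation.

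**Step 3: bias in Day 7 minus Day 0.** Bias = d × (difference in mean position)/19.
- Consecutive fives: d × 15/19 = 0.39, 0.79 and 1.58 SD for d = 0.5, 1 and 2.
- Rotation: d × 3/19 = 0.08, 0.16 and 0.32 SD.
- Either form of randomisation: zero on average.

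The standard error of a difference between two means of five is √(2/5) = 0.63 SD. With consecutive fives, the bias exceeds one standard error at d = 1. Under rotation it is a quarter of a standard error (0.16/0.63).

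**Step 4: false-positive rate.** The plan names no test for differences between biopsy days, so a one-way ANOVA across the four days at 0.05 serves as an illustration (10,000 simulated data sets per cell, no true day effect).

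| Rule | d = 0.5 | d = 1 | d = 2 |
|---|---|---|---|
| Consecutive fives | 7.2% | 13.7% | 45.7% |
| Rotation | 5.0% | 4.1% | 1.9% |
| Simple randomisation | 4.5% | 5.2% | 5.1% |
| Permuted blocks of four | 4.8% | 3.6% | 1.3% |

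The simulated biases (0.387, 0.781 and 1.575 SD for consecutive fives; 0.067, 0.154 and 0.308 SD for rotation) agree with Step 3 within simulation error. Rates fall below 5% under rotation and blocking because the drift is spread within each day and enlarges the residual variance.

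**The case against.** The strongest reply is that the wording also permits rotation. Rotation ties day to entry order less closely (R-squared 0.04) than simple randomisation is expected to (0.16), and it does not raise the false-positive rate. That stands. On that reading, what remains is a predictable sequence and a small residual trend.

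A second reply is that IV.D justifies the biopsy as showing the local response by prior vaccine, and that IV.G plans gene-expression comparisons between vaccine groups at each day. One rule governs both cohorts, so a drift shared by position largely cancels in a same-day ZVL versus RZV comparison, unless the cohorts enrol at different times. That also stands. It does not dispose of the point, because the Significance section and IV.H both name the timing of local events as something to be learned, and IV.G relates biopsies to blood across time points.

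A third reply is that the drift is assumed and no selection mechanism is shown. This is fair: at d = 0.5 even consecutive fives give a false-positive rate of only 7.2%. During the biopsy phase every enrolee must accept a biopsy, which limits selection although it does not prevent staff from timing entry.

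Systematic filling does guarantee five per day, but so do permuted blocks of four.

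**Conclusion.** The point holds conditionally. Biopsy day is set by entry order without randomisation, and the sequence is left open. Two coordinators could both follow the protocol and produce designs with an R-squared of 0.94 or 0.04 between entry order and day. If days are filled in consecutive fives, the bias in Day 7 minus Day 0 is 0.79 SD per 1 SD of drift. The age and gender adjustment would correct it only as far as those two variables account for the drift. If days rotate, the bias is 0.16 SD per 1 SD of drift and matters little.

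A reader might infer that the skin time course is confounded as planned, or that day and enrolment effects cannot be separated at all. The documents do not support either, because the sequence is not stated and no drift is documented. Nor do they make the time course the stated reason for the biopsies.

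The effect is confined to secondary between-day skin comparisons and to correlations pooled across days. The primary DNAemia comparison does not depend on biopsy day. This is a low-severity point, worth raising because the better rule is almost free.

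**What to change.** In IV.C, Part A, replace the entry-order clause with wording such as: *Biopsy day will be allocated at random within each vaccine cohort, in permuted blocks of four (one each of Day 0, 1, 3 and 7), from a concealed list; a replacement takes the day of the participant replaced.*

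Five blocks of four give 20 per cohort with exactly five per day, so the planned numbers do not change. The list should be held by someone who does not enrol participants, and each allocation revealed only after consent and eligibility are confirmed at Visit 1. Anyone tracking allocations could still deduce the last place in a block, but that is far less predictable than a fixed sequence.

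The cost is one 40-line list, with no extra biopsies, visits or staff.

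If biopsies have already begun, report the sequence actually used and add entry order to a sensitivity analysis. If consecutive fives were used, say that adjustment cannot reliably separate day from entry order, since only about 6% of the variation in entry position lies within days (1 − 0.94).

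Randomising the day does not remove the difference in site at Day 0, where the sample is unchallenged skin from the other arm. That should be stated as a limitation of any contrast with Day 0.

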### **Schedule of Events – Cohorts 1 & 2**

Cohorts 1 and 2 ZVL/RZV > 5y previously	Visit 1	Visit 2	Visit 3	Visit 4	Phone	Visit 5	Visit 6
	Day 0	Day 1	Day 3	Day 7 (+3)	+ 48 hour after V4	Day 60 (+30)	Day 120 (+30)
Informed consent, review of eligibility criteria	•						
Medical history and current medications	•					• 	• 
Blood draw (60ml)	•	•	•	•			
Pre-vaccination body temperature	•					• 	• 
Vaccination (ID vOka challenge)	•						
Punch biopsy of ID challenge site 	•  , or	•  , or	•  , or	• 			
Vaccination – Dose 1 RZV 						• 	
Vaccination – Dose 2 RZV 							• 
AE assessment	•	•	•	•	•		

40 subjects (20 in each vaccine group) with 5 each at one of the time points identified

Contralateral site only

If prior ZVL

Recruitment – There are very few people in the world who had RZV administered 5 years previously. These subjects will come from an experiment done here (COMIRB #13-3192) in which we compared immune responses to RZV and ZVL. The 4y post-vaccination samples are being collected this year, and the 5y sampling will be completed between Nov 2019 and Mar 2020. When these older vaccinees complete 5y after immunization, they will constitute a unique population eligible for our proposal. To secure participation for this proposal, we will contact participants in our current trial (who had consented to be contacted about future clinical trials).

### **Part B; Cohorts 3 and 4 – No Previous HZ vaccine**

Part B measures VZV DNAemia and systemic VZV-specific immune responses after ID vOka challenge in individuals who received HZ vaccines 6 months prior to the injection.

**Cohort 3** (n=35) subjects will be vaccinated with ZVL at enrollment; blood will be obtained at Days 0, 1, 3, 7 and 30 days after. Five - six months after receiving ZVL subject will be challenged with vOka administration (as described in Part A) followed by visits 1, 3, and 7 days later at which blood is drawn. Total of 9 to 11 visits.

These subjects will also be offered RZV vaccine (to comply with ACIP recommendations for shingles immunization) to be administered  $\geq$  60 days after vOka challenge. If subject wishes to receive the RZV vaccine, 2 additional visits will be required 2 beginning 2 months after Visit 6, increasing the duration of participation up to 10 months. Subjects will not be reimbursed for these visits but will receive the vaccine free of charge.

### **Schedule of Events – Cohort 3**

Cohort 3 – No Previous HZ Vaccine (to be admin ZVL)	Visit 1	Visit 2	Visit 3	Visit 4	Phone	Visit 5	Visit 6	Visit 7	Visit 8	Visit 9	Phone	Visit 10	Visit 11
	Day 0	Day 1	Day 3	Day 7	Day 9 (+3)	Day 30 (+7)	Day 150 (+44)	Day 151	Day 153 (+2)	Day 157 (+10)	+48 hours	60 Days after V6 (+30)	60 days after V10 (+30)
Informed consent, review of eligibility criteria	●												
Medical history and current medications	●						●						
Blood draw (60ml)	●	●	●	●		●	●	●	●	●			
Pre-vaccination body temperature	●						●						
Vaccination – Zostavax	●												
Vaccination (ID vOka challenge)							●						
AE assessment	●	●	●	●	●	●	●	●	●	●			
Vaccination – Dose 1 RZV 											● 		
Vaccination – Dose 2 RZV 												● 	

If subject wishes to receive RZV

**Cohort 4** (n=35) subjects will be enrolled, have blood (60ml) drawn, and will be administered RZV (2 doses –D0, D60) prepared and administered in accordance with the package insert, in the clinic. Participation will consist of 10 visits over the course of approximately 9 months. Blood will be drawn at Day 0, Days 61, 63, 67, and 90. These subjects will receive the challenge dose of vOka 6 months later at Day 240, with blood drawn, then drawn again at Days 241, 243, 247. Participation will consist of 10 visits over the course of approximately 8.5 months.

### Schedule of Events – Cohort 4

Cohort 4 – No Previous HZ Vaccine (to be admin RZV)	Visit 1	Phone	Visit 2	Visit 3	Visit 4	Visit 5	Visit 6	Visit 7	Visit 8	Visit 9	Visit 10	Phone
	Day 0	Day 7 (+3)	Day 60 (+14)	Day 61	Day 63	Day 67 (+3)	Day 90 (+7)	Day 240 (+14)	Day 241	Day 243	Day 247 (+3)	+48 hours after V 5, 6, 10
Informed consent, review of eligibility criteria	●											
Medical history and current medications	●		●					●				
Blood draw (60ml)	●		●	●	●	●	●	●	●	●	●	
Pre-vaccination body temperature	●		●					●				
Vaccination – Dose 1 RZV	●											
Vaccination – Dose 2 RZV			●									
Vaccination (ID vOka challenge)								●				
AE assessment	●	●	●	●	●	●	●	●	●	●	●	

### D. Description, Risks, and Justification of Procedures and Data Collection Tools

#### Risks

Zostavax- The risks are those associated with a licensed vaccine for people 50 years and older. Subjects will be given the relevant Vaccine Information Sheet (VIS).

ID vOka challenge (as 1 dose of licensed ZVL; Zostavax) –The intradermal route was previously studied in ~200 subjects without a noteworthy safety signal (13). The device for ID administration is licensed and was used in a prior study (COMIRB #11-1210). Some subjects will be receiving ZVL for the second time. There is no recommendation for a second dose of ZVL, but we completed a study (COMIRB #10-1461) in which 200 participants safely received a second dose of ZVL. Furthermore, ZVL is recommended after prior herpes zoster, which is analogous to re-exposure (as with our ID challenge) to the virus of herpes zoster. Very rarely, a brief, painless blistery rash limited to the site of injection may develop.

Shingrix – This vaccine will be administered according to the package insert. The risks are those associated with a licensed vaccine for people 50 years and older. Subjects will be given the Vaccine Information Sheet (VIS).

As with all vaccines or drugs, rarely an allergic reaction could occur – a rash, hives or even difficulty breathing.

Risk of receiving multiple shingles vaccines – two doses of RZV have been safely administered to prior ZVL recipients, and also to individuals who had prior HZ. This was done prior to licensure and mentioned in the ACIP recommendation, indicating no concern with an aberrant immune response in this setting.

Blood draws – 60 ml of blood will be taken at each blood draw for a total of 240 ml in 1 week for subjects in Cohorts 1, 2, 3 and 4. Subjects in Cohort 3, receiving ZVL, will have a total of 540 ml drawn over the course of the study. Subjects in Cohort 4, receiving RZV, will have a total of 600 ml drawn, over the course of the study. Neither will have more than 240 ml drawn in a week. The risks of phlebotomy are minimal and include pain, swelling, bruising, or infection around the vein, although this is very uncommon.

Punch biopsy – The skin biopsy will be taken at the ID vOka challenge site (except for Day 0 participants, in which case it will be done on the contralateral arm). The area will be numbed; then a punch biopsy device will be pressed into the skin removing a small circle of skin.

Risks include local pain, potential for infection, and scarring at punch site, and possible allergic reaction to the numbing medicine. This procedure is being overseen by a dermatologist skilled in this procedure. This procedure is important because it will indicate what the local immune response to the herpes zoster virus is in people who previously received either ZVL or RZV.

Genetic testing – In order to do epitope mapping and to create tetramers we will do HLA typing of white blood cells.

### **Benefits**

There is no known benefit from this study, but this research may influence future decisions made by participants concerning booster doses of HZ vaccine. It may also lead to improved vaccines for older persons. ID ZVL may further enhance protection. This is likely, but is unstudied. Some participants may receive RZV, which is recommended to prevent herpes zoster.

### **E. Safety Reporting**

For this study, adverse events (AE) will be collected for 48 hours after each study procedure and for 7 days after vOka administration. Additionally, AEs will be collected for 7 days after administration of ZVL to Cohort 3, and RZV to Cohort 4 participants. Participant will be asked at each visit: “Have there been any significant changes to your health since we saw you last? New medications? Hospitalizations?”

An adverse event will include any untoward or unfavourable medical occurrence associated with:

- **Study intervention:** ID vOKA – AEs starting within 7 days after injection and Grade  $\geq 3$  will be recorded and followed until resolution. ZVL – Subjects in Cohort 3 receiving ZVL on Day 0 will be followed for AEs for 7 days. RZV – Subjects in Cohort 4 receiving RZV on Day 0 and Day 60 will also be followed for AEs for 7 days after each injection. Any Grade  $\geq 3$  will be recorded and followed until resolution.
- **Study mandated procedures:** blood draw, skin biopsies and injections – Any AE, Grade  $\geq 3$ , occurring within 48 hours at the site of vOKA injection, skin biopsy or venipuncture will be recorded and followed until resolution. (This excludes optional RZV vaccination for participants in Cohorts 1 and 3.)

Adverse events will be graded on a scale from 1 to 5 according to the following:

Grade 1 = mild adverse event.

Grade 2 = moderate adverse event.

Grade 3 = severe and undesirable adverse event.

Grade 4 = life-threatening or disabling adverse event.

Grade 5 = death.

The PI will review AEs on a continuous basis during the study. Both Zostavax and Shingrix are FDA-approved vaccines that have been extensively studied. While no unusual vaccine-related SAEs are anticipated, we propose the following halting rules for risk management. The PI will be responsible for responding to vaccine-related serious adverse events. Reporting will be to the manufacturers of each vaccine, the IRB, and to the NIH Medical Monitor (as required).

